2.4 Sample size calculation

Based on current RSA studies and the high degree of sensitivity and accuracy of measurements of migration, relatively small patient groups should show statistical significant outcome.(22) A standardized phantom experiment for the model-based RSA, was performed with an acetabulum cup (Delta-TT cup, LINK) under simulated *in-vivo* conditions (Table 1). In such a phantom experiment, there is no actual movement between the components and the bone, therefore, the observed relative motions represent the

measurement error of these specific components using model-based RSA. These standard deviations are good estimations for the accuracy of the method that can be achieved *invivo*. The relative motions presented in table 1 are smaller than the accepted relative motions presented by Baad-Hansen et al.(23)

Table 1: Relative motions of the Delta-TT cup with respect to the acetabulum bone markers calculated using the elementary geometric shape (EGS) model (n = 10).

	Translations (mm)			Rotations (deg)			
	Trans (x)	Long (y)	Sag (z)	Trans (x)	Long (y)	Sag (z)	
Mean	0.001	0.003	-0.009	-0.069	-0.033	0.033	
St. dev	0.094	0.041	0.074	0.182	0.276	0.396	
Min	-0.145	-0.048	-0.113	-0.410	-0.493	-0.833	
Max	0.170	0.098	0.101	0.137	0.314	0.618	

Sample size calculation based on a t-test was done, assuming normal distribution of migration data and standard deviation of translation of 0.3 mm within the patient collective at two years follow-up.(23) When the sample size in each group is 25, a two group 0.05 t-test will have 90% power to reject the null hypothesis that the two cups are not equivalent (= the difference in means, is 0.3 mm or farther from zero in the same direction) in favour of the alternative hypothesis that the means of the two groups are equivalent, assuming that the expected difference in means is 0 and the common standard deviation is 0.3 mm. This difference of 0.3 mm translation can be considered as a clinically relevant difference.

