6. METHODS

6.1 Study parameters/endpoints

6.1.1 Main study parameter/endpoint

Migration of the acetabular cup at two year postoperative, measured with RSA and CT. RSA X-rays will be collected at discharge, 6 weeks, 6 months, 1 year and 2 years after surgery. Low-dose CT scans of the hip will be collected at discharge and 2 years after surgery.

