6.3.1 RSA procedure

The RSA set-up consist of two synchronized roentgen tubes positioned approximately 1.5 meter above two roentgen cassettes (35 X 43 cm) at a 20° angle to the vertical. Both roentgen tubes simultaneously expose the roentgen film (Figure 2). A calibration box is used to calibrate the experimental set-up.

The RSA X-ray which is taken one or two days after surgery (before loading) is used as baseline. Since the tantalum beads are fixed in the bone around the implants, the position of the implant relative to the bone can be calculated. Taking these bone markers as reference points, the spatial translations and rotations of the component during follow-up can be calculated.(22, 29) The bone markers need to be well fixated in the bone. Bone markers are defined unstable when they move more than 0.3 mm with respect to the other bone markers. Unstable markers will be excluded from analysis.(30) When there are not enough markers visible in the baseline RSA X-ray and this does not improve by placing the patient in another position, the patient will be excluded from the study (secondary exclusion criterium).

[figure not shown]

Figure 2: A uniplanar RSA arrangement. Two X-ray tubes are focused on the joint under examination. A calibration cage is placed underneath the X-ray table. It holds two X-ray films positioned next to each other.(22)

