8. STATISTICAL ANALYSIS

Descriptive data will be summarized by treatment group. For parameters represented by continuous variables, the summaries will consist of the mean, median, standard deviation, interquartile range, minimum, and maximum values. For categorical variables, the number and percentage in each category will be presented.

Continuous outcome variables and their differences will be analysed with parametrical statistical techniques, unless the normality assumption does not seem reasonable for the data, in which case non-parametric techniques will be considered. A two-sided 0.05 alpha level will be used.

A paired t-test will be used to measure the differences in translations and rotations between RSA and CT.

Actions will be taken to minimize the amount of missing data. If data is missing, this will be handled according to the instructions of the specific measurement instrument, or if not available, imputation techniques will be used to replace the missing data.

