8.1 Primary study parameter(s)

The main study parameter is the early migration (translational and rotational movements) of the BiMobile 2 mm cement acetabular cup and the BiMobile 4 mm cement acetabular

Version number: 3.0, date 20-12-2021 23 of 31

cup after two years. RSA data (discharge, 6 weeks, 6 months, 1 year and 2 years postoperatively) will be analysed using repeated measures ANOVA or mixed models if certain data points are missing. The null hypothesis is that there is no significant difference in mean migration at all time points. The alternative hypothesis is that the mean migration is significantly different at one or more time points.

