8.2 Secondary study parameter(s)

Secondary study parameters concern physical functioning, quality of life, pain, patient satisfaction, device-related complications, reoperations and implant survival. Furthermore, early migration will be compared between the BiMobile 2 mm cement acetabular cup and the Avantage 2 mm cement acetabular cup. The secondary outcomes, will be analysed in the same manner as the primary study parameter, except for implant survival, which will be analysed using Cox regression analysis.

CT data (discharge and 2 years postoperatively) will be analysed using repeated measures ANOVA or mixed models if certain data points are missing.

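### The main endpoint and the sample size are set at two years, but the primary hypothesis is met by a difference at any visit and no two-year contrast is named

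*Protocol*

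**What the plan says.** - **Endpoint.** Section 6.1.1 gives the main parameter as "Migration of the acetabular cup at two year postoperative, measured with RSA and CT". The Summary also places it at two years.
- **Sample size.** Section 2.4 uses the SD at two years (0.3 mm for translation, 0.8 degree for rotation). For 25 patients per arm it states: "a two group 0.05 t-test will have 90% power to reject the null hypothesis that the two cups are not equivalent".
- **Primary analysis.** Section 8.1 compares the two BiMobile groups. It puts RSA data from discharge, 6 weeks, 6 months, 1 year and 2 years into a repeated measures ANOVA, or a mixed model if data points are missing. The null is no difference at all time points. The alternative is: "The alternative hypothesis is that the mean migration is significantly different at one or more time points". Section 8 adds: "A two-sided 0.05 alpha level will be used".
- **Objective.** The Summary words the comparison as migration *at* two years; section 1 words it as migration *up to* two years.
- **Reference film.** Section 6.3.1: "The RSA X-ray which is taken one or two days after surgery (before loading) is used as baseline". Table 2 schedules no earlier RSA film.
- **Missing data.** Where no instrument rule exists, section 8 says "imputation techniques will be used to replace the missing data"; section 8.1 turns to a mixed model.

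**The concern.** The endpoint and the sample size ask about mean migration at one time. The hypothesis in section 8.1 asks whether the group means differ at any of several times. These questions can have different answers. If the groups differ at 6 weeks and converge by two years, section 8.1 counts a positive primary result although the endpoint shows no difference.

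Section 8.1 also does not say which ANOVA term carries the decision. The group-by-time or joint test responds to a difference at any visit. The group effect averages the visits and can miss a difference that opens late. The same data could thus support different primary conclusions depending on which line of the output is read.

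**Working it through.** **Inputs from the protocol:** n = 25 per group; SD 0.3 mm and difference of interest 0.3 mm at two years (section 2.4); two-sided 0.05 (section 8).

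**Assumed, not in the protocol:** correlation ρ of 0.6 to 0.8 between follow-up visits, either decaying as ρ^|i−j| or equal for all pairs; SD either 0.3 mm at every follow-up visit or rising 0.15, 0.20, 0.25, 0.30 mm.

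**Step 1. The plan's own figure.** The standardised ratio is 0.3 / (0.3 × √(2/25)) = 3.536. Normal-approximation power for equivalence is 2Φ(3.536 − z) − 1.
- 0.025 per side: 2Φ(3.536 − 1.960) − 1 = 88.5% (exact t 86.7%).
- 0.05 per side: 2Φ(3.536 − 1.645) − 1 = 94.1% (exact t 93.4%).

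The stated 90% lies between these, so the figure reproduces. It is a two-year calculation. Rotation has the same ratio (0.8/0.8).

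**Step 2. A two-year contrast.** As a two-sided difference test on 48 degrees of freedom with noncentrality 3.536, power for 0.3 mm is 93.4%. At the floor of 20 per group in section 6.5, noncentrality is 1/√(2/20) = 3.162 and power 86.9%. Type I error is 5% whatever happens at earlier visits.

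**Step 3. Difference of 0.3 mm at 6 weeks only, none at two years.** A joint test of the four follow-up differences is F on 4 and 45 degrees of freedom, with noncentrality λ = (n/2) d′Σ⁻¹d. With constant SD:
- decaying correlation: λ = 12.5 / (1 − ρ²)
- equal correlation: λ = 12.5 (1 + 2ρ) / [(1 − ρ)(1 + 3ρ)]

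| Correlation | ρ | λ | Joint test rejects | Two-year contrast rejects |
|---|---|---|---|---|
| decaying | 0.6 | 19.5 | 93.7% | 5% |
| decaying | 0.7 | 24.5 | 97.8% | 5% |
| decaying | 0.8 | 34.7 | 99.8% | 5% |
| equal | 0.6 | 24.6 | 97.8% | 5% |
| equal | 0.8 | 47.8 | about 100% | 5% |

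With rising SD the 6-week SD is halved, so λ is four times as large and rejection is almost certain. In simulation over a wider range of ρ (0.3 to 0.9), the group-by-time test rejected in 84-100% of trials.

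**Step 4. Difference that opens late.** Take 0, 10%, 40% and 100% of 0.3 mm at 6 weeks, 6 months, 1 year and 2 years. The averaged difference is (0 + 0.03 + 0.12 + 0.30)/4 = 0.1125 mm. Noncentrality of the group effect is 0.1125 / (SD of a patient's mean × √(2/25)).

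| SD pattern (decaying correlation) | ρ | SD of patient mean | Noncentrality | Power, group effect |
|---|---|---|---|---|
| constant | 0.6 | 0.231 | 1.72 | 39% |
| constant | 0.8 | 0.264 | 1.51 | 31% |
| rising | 0.6 | 0.175 | 2.27 | 61% |
| rising | 0.8 | 0.199 | 2.00 | 50% |

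Equal correlation gives 29-34% (constant SD) and 47-54% (rising SD). The two-year contrast has 93.4% throughout. A steeper rise (0.10, 0.17, 0.24, 0.30 mm) lifts the group effect to 55-68%, still well short.

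**Step 5. No difference at any visit.** In simulation, the multivariate or sphericity-corrected omnibus test rejected in 4.5-5.4% of trials. It is valid for its own null.

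**The case against.** **The test is not invalid.** A reader might infer that the primary analysis breaks the 5% level outright. It does not: a joint or corrected omnibus test keeps 5% for the null that section 8.1 states. Four separate visit tests would reject at least once in 9-18% of null trials (1 − 0.95⁴ = 18.5% if independent), but the protocol plans one model, not four tests. This objection stands.

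**The two failings belong to different readings.** The early false lead arises with the joint or group-by-time test, the missed late difference with the averaged group effect. Both cannot occur with one chosen term. This is correct, and the wording about one or more time points fits a joint test better. But section 8.1 does not choose, and neither term is the two-year comparison.

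**Section 1 says up to two years,** which suits a longitudinal hypothesis. That is fair, and it shows that the protocol is divided on its question. The Summary, section 6.1.1 and the sample size all point to two years.

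**An unseen SAP may name the contrast.** It may, but section 8.1 states the hypotheses explicitly, and such an SAP would contradict them.

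**Discharge.** One might infer that including the discharge film weakens the group test. It does not: a column of zeros scales each patient's mean and its SD by the same 4/5. Listing discharge may simply describe the films needed to compute migration.

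**CT.** Section 8.2 says "CT data (discharge and 2 years postoperatively) will be analysed using repeated measures ANOVA". One might call this faulty because, if the discharge scan is the reference, only one migration value per patient remains. The group and group-by-time F statistics then both equal the squared t on the two-year value, so nothing is lost.

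**Missing data.** One might infer inflated error from imputation. No imputation method is named, so no error rate can be attached. The natural reading is that the specific rule in section 8.1 governs RSA data, though the text does not say so.

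**Conclusion.** The concern holds as a mismatch between hypothesis and endpoint. Section 8.1 lets a difference at any visit decide a question that the Summary, section 6.1.1 and section 2.4 place at two years. Under the assumed correlations (0.6 to 0.8) and SD patterns, a 6-week-only difference of 0.3 mm gives a positive joint test in about 93-100% of trials, against 5% for the two-year contrast. Read as the averaged group effect, the analysis finds a late-opening 0.3 mm difference in about 30-60% of trials, against about 93%.

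The exact percentages depend on correlations, SD patterns and difference profiles that the protocol does not give. The mismatch itself rests on the text alone. The documents do not support the wider claims that the omnibus test is invalid for its own null, that discharge dilutes the group effect, or that the CT analysis is wrong. The contrast between an equivalence sample size and a difference hypothesis, and the choice among translation and rotation axes, are separate matters not judged here.

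**What to change.** 1. In section 8.1, restate the primary hypothesis as the difference between groups A and B in mean migration at two years, reported with its confidence interval.
2. Estimate it from a mixed model with group, visit and group-by-visit on the 6-week, 6-month, 1-year and 2-year values, with visit-specific variances. State that discharge is the zero reference and not a response.
3. Describe earlier visits as supportive.
4. State that the mixed model on observed data governs missing RSA values, so that the general imputation sentence in section 8 does not apply to them.
5. Align the time wording in the Summary and sections 1, 6.1.1 and 8.1.

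The cost is wording only, with no extra patients, films or visits. The one loss is that a difference seen only at an early visit can no longer be presented as the primary result.

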8.2 Secondary study parameter(s)

Secondary study parameters concern physical functioning, quality of life, pain, patient satisfaction, device-related complications, reoperations and implant survival. Furthermore, early migration will be compared between the BiMobile 2 mm cement acetabular cup and the Avantage 2 mm cement acetabular cup. The secondary outcomes, will be analysed in the same manner as the primary study parameter, except for implant survival, which will be analysed using Cox regression analysis.

CT data (discharge and 2 years postoperatively) will be analysed using repeated measures ANOVA or mixed models if certain data points are missing.

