5.4 Summary of known and potential risks and benefits

The Avantage cup is already used in standard care in most hospitals in The Netherlands. The ODEP rating 5A and NOV rating 1B indicate that this implant can be used in usual care.(15, 16) Revision rate at five years postoperative 4.0% (3.0-5.3).(11)

- 5.5 Description and justification of route of administration and dosage Not applicable
- **5.6** Dosages, dosage modifications and method of administration Not applicable
- **5.7 Preparation and labelling of Non Investigational Medicinal Product**Not applicable
- 5.8 Drug accountability

Not applicable

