6.1.2 Secondary study parameters/endpoints (if applicable)

Physical functioning, quality of life, pain and patient satisfaction will be scored with PROMs, consisting of: numeric rating scale (NRS) for pain in rest and during loading, Hip disability and Osteoarthritis Outcome Score Physical Short form (HOOS-PS), EQ-5D and an anchor question about general daily functioning. All PROMs will be collected prior to surgery, at 6 months, 1 year, 2 years and 5 years after surgery. All implant related (serious) adverse events including reoperations and survival of the THA (cup and stem component) will be collected up to 5 years after surgery.

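### Section 8.2 sends complications and reoperations to repeated measures ANOVA, and implant survival to a Cox model with about two revisions expected per two-arm comparison

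*Protocol*

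**What the plan says.** Section 8.2 lists the secondary parameters as "physical functioning, quality of life, pain, patient satisfaction, device-related complications, reoperations and implant survival", and adds the migration comparison of BiMobile 2 mm with Avantage. It then gives one analysis rule with one exception: they "will be analysed in the same manner as the primary study parameter, except for implant survival, which will be analysed using Cox regression analysis".

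The method referred to is in section 8.1, where the RSA data "will be analysed using repeated measures ANOVA or mixed models if certain data points are missing". Its hypothesis is about means of a measured quantity over visits: "The null hypothesis is that there is no significant difference in mean migration at all time points".

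Section 6.1.2 has implant-related adverse events, including reoperations, collected for 5 years, together with "survival of the THA (cup and stem component) will be collected up to 5 years after surgery". In Table 2 (section 6.3) adverse device events may be recorded at any time and are not tied to visits.

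The only 5-year revision rate with an interval is in section 5.4, for Avantage: "Revision rate at five years postoperative 4.0% (3.0-5.3". Section 4.3 states that BiMobile has not yet been studied clinically.

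**The concern.** A complication or reoperation either happens to a patient or does not, at a time of its own, and in this trial most patients will have none. Repeated measures ANOVA compares means of a roughly normal quantity measured on everyone at fixed visits. Applied to sparse yes/no data it gives standard errors and p-values that cannot be relied on.

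Implant survival has the right type of model but hardly any events. If one arm of a comparison has no revision, the Cox estimate runs off to zero or infinity and its Wald interval says nothing.

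These outcomes matter because this is the first clinical trial of the cup, and section 7.5 sets up no DSMB. Revision, reoperation and complications are the trial's main clinical safety results, and section 8.2 is the text that fixes how the groups are compared on them.

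**Working it through.** **Part 1: which method applies to complications and reoperations.** This is a matter of reading, not arithmetic.

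- Section 8.2 names both outcomes as secondary and exempts only implant survival, so both fall under the section 8.1 method.
- The mixed-model alternative in section 8.1 depends on missing data, not on the type of outcome. With complete data the rule gives ANOVA.
- The opening of section 8 provides a non-parametric fallback, but for continuous outcomes only.
- The same paragraph provides numbers and percentages for categorical variables. That is a summary by group, not a comparison between groups, and it does not replace section 8.2.

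No other section gives these two outcomes a different comparison.

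**Part 2: how many revisions the Cox model would have.** Section 8.2 states no event count, so there is no figure of its own to reproduce. The sample size in section 2.4 was set for migration and enters here only as n = 25 per group.

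Inputs: n = 25 (sections 2.4 and 3); 5-year revision rate p = 4.0%, range 3.0-5.3% (section 5.4, Avantage). Applying p to BiMobile is an assumption.

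Expected revisions are n × p per group and 2 × n × p per two-arm comparison. The chance that a given arm has none is q = (1 − p)^25. The chance that at least one of two arms has none is 1 − (1 − q)².

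| p | per group | per two arms | q | at least one of two arms empty |
|---|---|---|---|---|
| 3.0% | 0.75 | 1.5 | 0.97^25 = 0.467 | 1 − 0.533² = 72% |
| 4.0% | 1.0 | 2.0 | 0.96^25 = 0.360 | 1 − 0.640² = 59% |
| 5.3% | 1.3 | 2.65 | 0.947^25 = 0.256 | 1 − 0.744² = 45% |

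At 4.0% the 59% has two parts. Both arms are empty with probability 0.360² = 13%, and there is then nothing to estimate. Exactly one arm is empty with probability 59% − 13% = 46%, and the hazard ratio is then zero or infinite.

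**When both arms do have events.** With E events split evenly, SE(log HR) ≈ 2/√E. For E = 2 this is 1.41, and the 95% interval extends by a factor of exp(1.96 × 1.41) ≈ 16 either way. Power at a hazard ratio of 2 is Φ(ln 2 × √(2/4) − 1.96) = Φ(−1.47) = 7%; 80% power would need 66 events. A split of 3 v 0 in 25 v 25 gives a Fisher p-value of 0.23, 5 v 0 gives 0.0502, and 6 v 0 is the first below 0.05 (0.022).

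**Sensitivity.** Section 6.5 tolerates a fall to 20 per group. With 20 contributing full follow-up, q = 0.96^20 = 0.442 and the 59% becomes 1 − 0.558² = 69%. If BiMobile had twice the Avantage rate (8%, an assumption), a comparison of the two BiMobile arms would expect 4 revisions, q = 0.92^25 = 0.124, and the chance would be 1 − 0.876² = 23%. With 4 events the interval still extends by a factor of about 7.

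**The case against.** Several points on the other side are sound.

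- **Cox regression is a proper model for time to revision.** A reader might infer that it is the wrong type of model. It is not; the difficulty is the number of events. The trial was sized for migration and claims no power for survival. With one empty arm, a log-rank test and a one-sided profile-likelihood bound can still be computed. What fails is the hazard ratio with its Wald interval.
- **The 4.0% is an Avantage figure.** Two of the three arms receive BiMobile, and section 5.4 does not say that its rate uses the cup-and-stem definition of section 6.1.2. The event counts are therefore conditional.
- **Three arms.** A reader might quote the chance that at least one of the three groups has no revision: 1 − 0.640³ = 74%. That overstates the problem, because a comparison of the two other arms may still be estimable. The pairwise 59% is the relevant figure.
- **Raw counts will be visible.** Section 8 requires numbers and percentages by group, so it would be wrong to say that the plan hides the safety results. It does not cure the assigned comparison.
- **PROMs.** A reader might infer that the pre-operative score becomes one of five responses, since "All PROMs will be collected prior to surgery, at 6 months, 1 year, 2 years and 5 years after surgery" and the primary model includes the discharge reference among its time points. The protocol does not say so. The role of the baseline score is commonly left to a SAP, and a model with baseline as a time level does no harm if group-by-time contrasts are used. Dilution of a constant effect to 4/5 would apply only to a group effect averaged over five visits, which the protocol does not name.

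The reading of section 8.2 for complications and reoperations survives all of this. It is an explicit assignment of a method, not a detail left for later.

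**Conclusion.** The point holds in two parts of unequal strength.

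For device-related complications and reoperations, section 8.2 states the wrong method. This follows from the wording alone and needs no assumption.

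For implant survival, the model type is acceptable but unlikely to yield a usable hazard ratio. About 2 revisions are expected per two-arm comparison (1.5-2.65), with a 59% chance (45-72%) that at least one of the two arms has none. This assumes the Avantage rate in all arms, the same definition of revision, full 5-year follow-up of 25 per group, and independence between patients. Deaths and withdrawals would lower the counts.

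The documents do not support a claim that the PROM analysis is in error.

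All the outcomes concerned are secondary, and the migration result does not depend on them. The wording should be corrected before analysis.

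**What to change.** In section 8.2:

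1. Limit the reference to the primary method to the continuous outcomes, that is PROMs and migration.
2. Analyse device-related complications and reoperations as number and percentage of patients per group, with exact confidence intervals for the risk difference.
3. Report implant survival as revision counts per group and Kaplan-Meier estimates at 2 and 5 years with confidence intervals. Cumulative incidence with death as a competing event is an alternative, given the age of the patients and the 5-year follow-up. Any hazard ratio should come from a Firth-penalised fit and be labelled exploratory.

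As an optional clarification, not the correction of an error, the text could say that the pre-operative PROM score enters as a covariate and not as a response level.

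The cost is wording only, since the data are already to be collected. The one thing given up is a conventional Cox hazard ratio as the main survival result, which these numbers would seldom support.
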